Subject Population Key Criteria for Inclusion and Exclusion:	Inclusion criteria include adult kidney transplant candidates at the University of Minnesota or Hennepin County Medical Center. Exclusion criteria include inability to consent, non-English speaking, or candidates for combined organ transplant.		
Number Of Subjects	Total Number of Subjects: 60		
	Total Number of Sites: 2		
Study Duration	Each subject's participation will last 3 months.		
	The entire study is expected to last through November 1 st 2020.		
Study Phases	(1) Screening : screening for eligibility and obtaining consent		

Screening	(2) Intervention: group counseling session	
Intervention		
Follow-Up		
Efficacy Evaluations	Primary evaluation measurements that will be used to assess the efficacy of the intervention	
Pharmacokinetic Evaluations	Not applicable	
Safety Evaluations	Not applicable	
Statistical And Analytic Plan	A Student's T-test will compare means for the primaiy outcome of the number of inquiries per candidate (primary outcome). Chi- squai ed and Student's T-tests will be used to compare secondary outcomes.	
Data And Safety Monitoring Plan	The principle investigator is responsible for data quality management and ongoing assessment of safety.	

page1v

Study Phase	Screening	Treatment/Intervention	Follow-up
Visit Number	1	2	NIA
Informed Consent/Assent	Х		
Review Inclusion/Exclusion Criteria	Х		
Bassline Survey to measure secondru.y outcomes	Х		
Demographics/Medical Histo1y	Х		
Randomization	X		
Intelvention (group counselling session)		X	
Survey to measure secondru.y outcomes		X	
Assess primru.y outcome through medical records			Х

TABLE 1: SCHEDULE OF STUDY PROCEDURES

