5.2 Efficacy Evaluations

Baseline and outcome evaluations will be used to test for intervention efficacy. These measures will include: pursuit of transplant, patient knowledge about kidney transplant,

patient decisional conflict, patient hope, social support group knowledge about kidney transplant and social support group intention/motivation to support the patient through the transplant process. A process evaluation will be conducted to ensme the intervention is implemented with fidelity and to assess what worked and did not work dming the implementation process.

5.2.1 Diagnostic Tests, Scales, Measures, etc.

Baseline evaluations will be administered before pruticipation in the intervention. After the intervention is complete, the outcome evaluation smvey will be administered. These smveys will have the same questions and measurements (listed above) in order to test for intervention efficacy/effectiveness.

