6.3 Statistical Methods

A Student's T-test will compare means for the primaly outcome of the number of inquiries per candidate between and within the intervention and control groups. Both a Chi-squared and Student's T-tests will be used to compare secondruy outcomes between and within the intervention and control groups. This is a feasibility pilot study; therefore, it is not powered to test anything. We will be collecting data that we could adjust for (i.e. demographics), but we will not be adjusting, because the main goal of this particulru study is to gauge if the intervention is feasible.

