6.3.2 Efficacy Analysis

The primaly efficacy endpoint will be the change in pursuit of transplant between the baseline and the outcome evaluation. Secondary endpoints will include the change in patient knowledge about kidney transplant, patient decisional conflict, patient hope, social supp01t group knowledge about kidney transplant and social support group intention/motivation to support the patient through the transplant process between the baseline and outcome evaluation. All measurements will be compared with the control/no treatment group measurements.

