9 STUDY ADMINISTRATION

9.1 TREATMENT ASSIGNMENT METHODS

9.1.1 Randomization or Other Assignment

Randomization will be computer generated and stratified by site.

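### Minor: patient survey scores are to be compared by unadjusted t-tests of change, although ANCOVA on the baseline score already collected would usually be more precise

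*Protocol*

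**What the plan says.** Four places in the protocol bear on this.

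- **6.3 Statistical Methods** fixes the tests: "Both a Chi-squared and Student's T-tests will be used to compare secondruy outcomes between and within the intervention and control groups". It does not assign tests to endpoints. It then excludes adjustment, naming demographics as what could be adjusted for: "We will be collecting data that we could adjust for (i.e. demographics), but we will not be adjusting". The reason given is that feasibility is the main goal.
- **6.3.2 Efficacy Analysis** puts the secondary endpoints on the change scale: "Secondary endpoints will include the change in patient knowledge about kidney transplant", and likewise patient decisional conflict and hope. All are compared with the control group.
- **5.2.1** has a survey before and after the intervention: "These smveys will have the same questions and measurements (listed above". Table 1 schedules it at the screening visit and again at the intervention visit.
- **9.1.1**: "Randomization will be computer generated and stratified by site". There are two sites.

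**The concern.** No single sentence says that a t-test of change will be used. It follows from 6.3 (t-tests, no adjustment) and 6.3.2 (endpoints defined as change) for any patient scale that is treated as a continuous score. In the appendix these would be knowledge (items 1–9), hope (items 14–25) and, if its yes/no items are summed, decisional conflict (items 10–13).

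Subtracting the baseline score forces its coefficient to be 1. When the two scores are only moderately correlated, that subtracts too much and adds noise. ANCOVA estimates the coefficient instead. What is at stake is the width of the between-arm intervals for these scores and nothing else. The protocol plans these comparisons itself, and the baseline score is in hand, so precision is given up for no saving in data.

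**Working it through.** **Inputs.** From the protocol: two arms; 60 patients by 6.4 (30 at each of 2 sites, 2 × 30 = 60), or 15 by 3.3.2 (7 control + 8 intervention). Assumed, because the protocol gives none: equal SD at both times, a baseline–outcome correlation rho of 0.3 to 0.9, and two-sided 95% intervals. The plan has no figure for precision or power to reproduce.

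**Step 1, large samples.** In units of SD² × (1/n0 + 1/n1), the variance of the arm difference is
- t-test of change: 2(1 − rho)
- ANCOVA on baseline: 1 − rho²

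The ratio is (1 − rho²) / [2(1 − rho)] = (1 + rho)/2, which is below 1 for every rho below 1. Interval widths are in the ratio √((1 + rho)/2): 0.806, 0.866, 0.922 and 0.975 at rho 0.3, 0.5, 0.7 and 0.9.

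**Step 2, small-sample cost.** ANCOVA loses one degree of freedom and pays for chance baseline imbalance, which inflates the variance by 1 + 1/(N − 4) on average for a normal covariate.
- N = 60: √(1 + 1/56) = 1.009. The t quantiles on 57 and 58 df are practically equal. Factor 1.009.
- N = 15: √(1 + 1/11) = 1.044. The t quantiles are 2.179 (12 df) and 2.160 (13 df), ratio 1.009. Factor 1.044 × 1.009 = 1.053.

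**Step 3, width of ANCOVA (baseline only) relative to the t-test of change.** Simulations used normal scores and no site difference.

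| rho | 60 patients, formula | 60, simulated | 15 patients, formula | 15, simulated |
|---|---|---|---|---|
| 0.3 | 0.806 × 1.009 = 0.81 | 0.82 | 0.806 × 1.053 = 0.85 | 0.85 |
| 0.5 | 0.866 × 1.009 = 0.87 | 0.88 | 0.866 × 1.053 = 0.91 | 0.91 |
| 0.7 | 0.922 × 1.009 = 0.93 | 0.93 | 0.922 × 1.053 = 0.97 | 0.97 |
| 0.9 | 0.975 × 1.009 = 0.98 | 0.98 | 0.975 × 1.053 = 1.03 | 1.02–1.03 |

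Break-even is where (1 + rho)/2 = 1/factor². For 15 patients, 1/1.053² = 0.902, so rho = 2 × 0.902 − 1 = 0.80. For 60, 1/1.009² = 0.982, so rho = 0.96. With 15 patients the simulated ratios are nearly the same if allocation within site is not blocked, a point 9.1.1 leaves open: 0.847, 0.906, 0.967 and 1.021.

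**Step 4, the site term.** Simulated ratios to the t-test of change, blocked allocation, at rho 0.3 / 0.5 / 0.7 / 0.9. The site differences are assumed.

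| Patients | Site difference | Baseline only | Baseline + site |
|---|---|---|---|
| 15 | none | 0.847 / 0.908 / 0.965 / 1.022 | 0.860 / 0.922 / 0.978 / 1.037 |
| 15 | 0.5 SD | 0.860 / 0.918 / 0.970 / 1.024 | 0.860 / 0.922 / 0.981 / 1.038 |
| 60 | none | 0.814 / 0.876 / 0.931 / 0.983 | 0.814 / 0.877 / 0.931 / 0.983 |
| 60 | 0.5 SD | 0.826 / 0.882 / 0.937 / 0.983 | 0.814 / 0.875 / 0.933 / 0.983 |

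With 60 patients, site is harmless or slightly helpful. With 15 it costs about 1–2% of width when the sites do not differ and gains nothing at 0.5 SD. It helps only at a difference near 1 SD with rho of 0.5 or less.

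**Step 5, bounded scores.** Whole-number scores on ranges of 0–9, 12–48 and 0–4, with assumed means and SDs, behave alike. With 60 patients and baseline + site, the interval is 17–18% narrower at an observed rho of 0.31–0.34, 10–11% at 0.55–0.59, 4–6% at 0.74–0.79 and 0–2% at 0.89–0.95.

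**The case against.** **It is a feasibility pilot, declared not powered, and a t-test is defensible.** True, and this is why the point is minor. But 6.3 and 6.3.2 still commit to between-arm comparisons. If they are made, feasibility is no reason to leave a collected baseline score out of the model.

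**The sentence on adjustment concerns demographics.** This stands. Leaving demographics unadjusted is reasonable. A reader might infer that the sponsor considered and rejected the baseline score and site, but 6.3 mentions neither. Their absence follows from the named test and the change endpoints.

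**Covariate detail belongs in an SAP.** Often it does. Here the protocol has itself chosen the test and the scale and excluded adjustment, so the point is about a stated choice.

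**The number of affected endpoints is uncertain.** This stands. Sections 6.3 and 6.3.2 give no scoring, and decisional conflict may go to a chi-squared test. The point covers only scales analysed as continuous scores.

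**Stratification by site calls for a site term.** A reader might infer that site must be in the model whatever the size. With 15 patients the figures do not support that for these scores.

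**The primary outcome should be adjusted too.** This is tempting, but the protocol does not settle what that outcome is. Table 1 places it at follow-up only ("Assess primru.y outcome through medical records"), while 6.3.2 makes it a change: "The primaly efficacy endpoint will be the change in pursuit of transplant between the baseline and the outcome evaluation". Section 5.2 also lists pursuit of transplant among the baseline and outcome evaluations: "These measures will include: pursuit of transplant, patient knowledge about kidney transplant". No firm adjustment can be proposed until that is reconciled.

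**Conclusion.** The point holds as a minor, cheap improvement. For continuous patient scores, ANCOVA on the baseline score is usually more precise than the planned t-test of change. With 60 patients the interval is about 18% narrower at rho 0.3, falling to 2% at rho 0.9. With 15 patients it runs from about 15% narrower to 2–3% wider, with break-even near rho 0.8.

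The size rests on assumed correlations, equal SDs at the two times and scores treated as continuous. It also depends on which patient number is right. The documents do not support a stronger reading, that the planned comparison is biased or invalid: under randomisation an unadjusted comparison of change is neither, and no conclusion of the study turns on the choice.

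The point does not extend to the number of inquiries, family endpoints, chi-squared outcomes or within-group tests. The conflicts between 3.3.2 and 6.4 on sample size, and between Table 1 and 6.3.2 on the primary outcome, are separate matters to reconcile.

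**What to change.** In 6.3, replace the blanket statement on adjustment with: *Continuous patient scores (knowledge, hope, and decisional conflict if scored) are compared between arms at the outcome evaluation by ANCOVA with the baseline score of the same scale as covariate; demographics are not adjusted for.*

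In 6.3.2, define these patient endpoints as the outcome score compared between arms adjusted for baseline, and report mean change per arm descriptively.

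Once the sample size is reconciled, add site, the stratification factor, as a further covariate if there are 60 patients (6.4). With the 15 patients of 3.3.2, use the baseline score alone.

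The cost is a few sentences, with no new data or visits. The statistical downside is the lost degree of freedom and the charge for chance baseline imbalance, which make the interval about 2–3% wider with 15 patients if rho is near 0.9.

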6.3.1 Baseline Data

Baseline and demographic characteristics will be summarized by standard descriptive summaries (e.g. means and standard deviations for continuous variables such as age and percentages for categorical variables such as gender).

6.3.2 Efficacy Analysis

The primaly efficacy endpoint will be the change in pursuit of transplant between the baseline and the outcome evaluation. Secondary endpoints will include the change in patient knowledge about kidney transplant, patient decisional conflict, patient hope, social supp01t group knowledge about kidney transplant and social support group intention/motivation to support the patient through the transplant process between the baseline and outcome evaluation. All measurements will be compared with the control/no treatment group measurements.

6.3.3 Pharmacokinetic Analysis

Not applicable

6.3.4 Safety Analysis

Not applicable

6.4 Sample Size and Power

The sample size will be n=60, with 30 patients consented from each site. This is a feasibility pilot study; therefore, it is not powered to test anything.

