3.3.2 Total Number of Study Sites/Total Number of Subjects Projected

The study will be conducted at two investigative sites in the United States.

Recruitment will stop when approximately 60 subjects are consented (7 patients in the control group + 8 patients + 6-7 friends and family each in the intelvention group).

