6 STATISTICAL CONSIDERATIONS

The sample size (n=60) will be sufficient for conducting statistical analysis of the intervention. A Student's T-test will compare means for the primaly outcome of the number of inquiries per candidate. Both a Chi-squared and Student's T-tests will be used to compare secondaly outcomes.

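### Section 6.4 sets the sample size at 60 patients, but the itemised target in section 3.3.2 contains only 15, a fourfold difference in the n of the per-candidate primary comparison

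*Protocol*

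**What the plan says.** Four places in the protocol give the size of the trial.

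- **Section 6.4:** "The sample size will be n=60, with 30 patients consented from each site". The unit is patients.
- **Section 3.3.2:** "Recruitment will stop when approximately 60 subjects are consented", with the make-up in brackets: "7 patients in the control group + 8 patients + 6-7 friends and family each" in the intervention group. The unit is subjects, and most of them are not patients.
- **Synopsis, Number Of Subjects:** "Total Number of Subjects: 60", over two sites and without a split.
- **Section 6:** "The sample size (n=60) will be sufficient for conducting statistical analysis of the intervention". No unit is given. The next sentence names the Student's t-test for the primary outcome.

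The unit of the primary analysis is the candidate. Section 6 describes it as the "outcome of the number of inquiries per candidate", and section 6.3 plans to compare the "number of inquiries per candidate between and within the intervention and control groups". On allocation, section 9.1.1 says "Randomization will be computer generated and stratified by site". Sections 6.3 and 6.4 both add that this is a feasibility pilot without power for any test.

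**The concern.** Sections 6.4 and 3.3.2 both describe people consented, and both arrive at about 60, but they count different things. One reaches 60 with patients alone. The other reaches it with a small group of patients and a much larger group of their friends and family.

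Friends and family are proper subjects for the family-survey endpoints. They add nothing to an outcome measured once per candidate. A single total that mixes the two groups therefore does not give the n of the primary comparison, and section 6 sets that total directly beside the primary t-test.

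At stake is whether the primary comparison rests on about 30 patients per arm or on 7 and 8. That determines how precise the result can be and how recruitment is to be judged, which is a basic question for a feasibility pilot. In addition, if the stop at about 60 people is what governs, the number of patients depends on how many relatives join.

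**Working it through.** **Inputs.** Section 6.4: 30 patients per site. Section 3.3.2: two sites, 7 control patients, 8 intervention patients, and 6 to 7 friends and family for each intervention patient. Sections 6 and 6.3: the primary outcome is counted per candidate. The protocol gives no SD, confidence level or allocation ratio.

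**Step 1: reproduce 6.4.** 2 sites × 30 patients = 60 patients. The figure is internally correct.

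**Step 2: add up 3.3.2.**
- Patients: 7 + 8 = 15.
- Friends and family: 8 × 6 = 48 to 8 × 7 = 56.
- All people: 15 + 48 = 63 to 15 + 56 = 71.
- Patients as a share of all people: 15/71 = 21% to 15/63 = 24%.
- A total of exactly 60 would need (60 − 15)/8 = 5.6 relatives per intervention patient, slightly below the stated 6 to 7.

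**Step 3: compare.** 60/15 = 4.

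**Step 4: try to reconcile the two.**
- *The 3.3.2 breakdown read as per site.* Patients would be 2 × 15 = 30 and people 2 × 63 = 126 to 2 × 71 = 142. Neither matches 60.
- *Loss between consent and enrolment.* Both sections count people consented, and the 60 in 3.3.2 already includes relatives, so attrition does not explain the gap.
- *60 patients with relatives on top.* With equal arms (assumed), 30 intervention patients would bring 30 × 6 = 180 to 30 × 7 = 210 relatives, or 240 to 270 people. The synopsis total of 60 subjects would then be wrong.
- *Patients in 6.4 written for subjects.* This would align 6.4 with 3.3.2 and the synopsis, but no passage says so. Section 9.6 speaks only of patients giving consent.

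**Step 5: effect on the primary comparison.** Assume a two-sided 95% interval, a common SD, and 30 v 30 for the 60. The half-width for the difference in means, in SD units, is t(0.975, n1 + n2 − 2) × √(1/n1 + 1/n2).

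| Patients | df | t | √(1/n1 + 1/n2) | Half-width |
|---|---|---|---|---|
| 7 v 8 | 13 | 2.160 | 0.5175 | 1.118 SD |
| 30 v 30 | 58 | 2.002 | 0.2582 | 0.517 SD |

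Ratio: 1.118/0.517 = 2.16.

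For the within-arm change, the half-width is t(0.975, n − 1)/√n in SDs of the change: 0.92 for n = 7, 0.84 for n = 8 and 0.37 for n = 30. These three values are conditional. Section 6.3 plans a within-group comparison, but Table 1 schedules the primary outcome only at follow-up.

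**Step 6: a stop counted in people.** With equal arms, a strict stop at 60 people and 6 relatives per intervention patient, each arm has 60/(1 + 1 + 6) = 7.5 patients, 15 in all. With 7 relatives it has 60/(1 + 1 + 7) = 6.7, about 13 in all. The shift is small within the stated range and grows if fewer relatives come than planned.

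**The case against.** The strongest reply is that one loose word causes the conflict. The synopsis and 3.3.2 both speak of subjects, and 3.3.2 is the only place that itemises them. Section 6 gives no unit, so 6.4 stands alone in saying patients. The economical reading is 15 patients and about 60 people. That may well be what was meant, but it remains an inference. It also leaves section 6 calling n=60 sufficient immediately before a t-test that would have 7 and 8 patients.

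Second, the protocol disclaims power and says its main goal is feasibility, so no stated power or error rate becomes wrong. This is correct, and it is why no power figure is criticised here. It does not say how many patients will be recruited, and the primary objective in section 2.1 is still framed as whether the intervention increases pursuit of transplant.

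Several smaller points stand:
- The arithmetic in 6.4 is right. The fault is an inconsistency between sections.
- Section 3.3.2 prints the 7 and 8 openly, so the patient number can be found there.
- The sentence in section 6 may also be meant to cover the family-survey endpoints.
- A sum of 63 is loosely compatible with approximately 60.
- Stratifying by site does not require a target per site.
- The interval widths are illustrations, and the within-arm ones presuppose a baseline measurement that is not scheduled.

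None of these removes the conflict between 15 and 60 patients.

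**Conclusion.** The concern holds. As written, the protocol commits to 60 patients in one section and 15 in another, and nothing in it decides between them. The factor of 4 follows directly from the protocol's own numbers and needs no assumption.

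Under the assumptions in the working, the 95% interval for the between-arm difference would be about 2.2 times as wide with 15 patients as with 60. That ratio is mainly the square root of 4, with a small t correction. The documents do not show which count was intended. This must be fixed, because the number concerned is the n of the primary comparison and the trial's recruitment target.

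**What to change.** The sponsor should state which count was intended and then make these changes:

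- Give one number of patients per arm and per site, identical in the synopsis and in sections 3.3.2, 6 and 6.4.
- Report friends and family as a separate count.
- Express the point at which recruitment stops in patients.
- **If 15 patients were intended:** restate sections 6 and 6.4 as 7 to 8 patients per arm. Replace the claim that n=60 is sufficient with the expected precision, a half-width of about 1.1 SD under the stated assumptions. Present the primary comparison as an estimate with its confidence interval, which fits the protocol's own disclaimer of power.
- **If 60 patients were intended:** correct the 7 + 8 breakdown in 3.3.2 and the total in the synopsis, since relatives would come on top of the 60.

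The cost is wording in four places. It requires no extra patients, no new endpoint and no change of objective. If 15 is the answer, the stated size will look less favourable than it does now.

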6.5 Interim Analysis

Not applicable.

7 STUDY MEDICATION (DRUG, DEVICE, OR OTHER STUDY INTERVENTION)

7.1 Description

7.1.1 Packaging

Not applicable

7.1.2 Labeling

Not applicable

7.1.3 Dosing

Not applicable

7.1.4 Treatment Compliance and Adherence

Not applicable

7.1.5 Drug Accountability

Not applicable

8 SAFETY MANAGEMENT

8.1 Clinical Adverse Events

Clinical adverse events (AEs) will be monitored throughout the study by the principal investigator.

8.2 Adverse Event Reporting

Since the study procedures are not greater than minimal risk, SAEs are not expected. If any unanticipated problems related to the research involving risks to subjects or others happen during the course of this study (including SAEs) they will be repolted to the IRB in accordance with IRB Attachment GGG: Unanticipated Problems Involving Risks to Subjects or Others. AEs that are not serious but that are notable and could involve lisks to subjects will be summarized and submitted to the IRB at the time of continuing review.

8.3 Definition of an Adverse Event

An adverse event is any untoward medical occmTence in a subject receiving a test alticle and which the occmTence does not necessarily have a causal relationship with the treatment. An adverse event can therefore be any unfavorable and unintended sign (including an abn01mal laborato1y finding), symptom, or disease temporally associated with the use of the test alticle, whether or not related to the product.

All AEs (including SAEs) will be noted in the study records and on the case report f01m with a full description including the natme, date and time of onset, dete1mination of nonserious versus serious, intensity (mild, moderate, severe), duration, causality, and outcome of the event.

